### **1.2.1 Primary estimand(s)**

The estimand is the precise description of the treatment effect and reflects strategies to address events occurring during trial conduct which could impact the interpretation of the trial results (e.g. premature discontinuation of treatment).

The clinical question of primary interest is: what is the reduction in LDL-C, quantified by difference of mean percentage change from baseline at Day 150, in Chinese adults with low or moderate ASCVD risk and elevated LDL-C who are not on any lipid-lowering therapy, who receive inclisiran as monotherapy, compared to placebo, regardless of discontinuation from study treatment, if other lipid-lowering therapy were not taken, and where death due to CV or non-CV causes is considered an unfavorable outcome.

The primary estimand is described by the following attributes:

Population: Chinese adults with low or moderate ASCVD risk and elevated LDL-C who are not on any lipid-lowering therapy.

Endpoint: Percentage change from baseline at Day 150 in LDL-C.

Treatments of interest: Inclisiran as monotherapy compared to the use of placebo, regardless of study treatment discontinuation.

Handling of intercurrent events:

- Permanent discontinuation of study treatment will be handled with a treatment policy strategy, keeping treatment labels as assigned at randomization.

- Use of prohibited LLT (PCSK9 monoclonal antibodies taken before Day 150 visit assessment or other LLT taken within 30 days before Day 150 visit assessment) will be treated with a hypothetical strategy of what would happen had those LLT not been taken and those participants behaved like other participants in the same treatment group.
- Participants who died will be handled with a composite strategy; death is considered an unfavorable outcome.

Summary measure: the summary measure to be used is the difference of mean percentage changes.

Complete details on the statistical methods and inference, including missing data handling and sensitivity analyses are provided in [Section 2.5](#).

## **1.2.2 Secondary estimand(s)**

### **1.2.2.1 Secondary estimands for core part**

The secondary estimands for core part address the same clinical question as the primary estimand, albeit for different endpoints. They share the same population, intercurrent events, summary measure, as well as the same treatments as the primary estimand. They differ by the definition of the endpoints, these being:

- Absolute change in LDL-C from baseline at Day 150
- Percentage and absolute change in PCSK9, TC, HDL-C, non-HDL-C, ApoB, ApoA-1, Lp(a) and TG from baseline at Day 150

Complete details on the statistical methods and inference, including missing data handling and sensitivity analyses are provided in [Section 2.6](#).

### **1.2.2.2 Secondary estimands for extension part**

The clinical question of interest in extension part is: what is the reduction in LDL-C, quantified by mean percentage or absolute change from baseline at Day 330, in Chinese adults with low or moderate ASCVD risk and elevated LDL-C who are not on any lipid-lowering therapy, who receive inclsiran as monotherapy, regardless of discontinuation from study treatment, if other lipid-lowering therapy were not taken, and where death due to CV or non-CV causes is considered an unfavorable outcome.

The secondary estimand for extension part is described by the following attributes:

Population: Chinese adults with low or moderate ASCVD risk and elevated LDL-C who are not on any lipid-lowering therapy.

Endpoint: Percentage or absolute change from baseline at Day 330 in LDL-C for inclsiran group.

Treatments of interest: Inclsiran as monotherapy, regardless of study treatment discontinuation.

Handling of intercurrent events:

- Permanent discontinuation of study treatment will be handled with a treatment policy strategy, keeping treatment labels as assigned at randomization.

- Use of prohibited LLT (PCSK9 monoclonal antibodies taken before Day 330 visit assessment or other LLT taken within 30 days before Day 330 visit assessment) will be treated with a hypothetical strategy of what would happen had those LLT not been taken, and those participants behaved like other participants in the same treatment group.
- Participants who died will be handled with a composite strategy; death is considered an unfavorable outcome.

Summary measure: the summary measure to be used is the mean percentage or absolute change.

Complete details on the statistical methods and inference, including missing data handling and sensitivity analyses are provided in [Section 2.6](#).

## 2 Statistical methods

### 2.1 Data analysis general information

All analyses will be performed by Novartis or a designated CRO. The most recent version of SAS available in the statistical programming environment of Novartis or the designated CRO will be used for the analyses.

The core part analyses will be conducted after the core part database lock, when all randomized participants have completed the Day 180 visit (or have discontinued from the study). The data snapshot at the time of the core part database lock will be used for these analyses. The analysis cutoff date will be determined and documented prior to the core part database lock, and will be chosen based on the operational feasibility, as a calendar date on or after the last core part visit date from all participants and prior to the core part database lock date. The analysis cutoff date will be applied to include relevant extension part assessments / events in the core part analyses. All events with start date before or on the cut-off date, and end date after the cut-off date will be reported as 'ongoing'. The same rule will be applied to events starting before or on the cut-off date and not having documented end date. The results from the core part analyses will be summarized in the core part CSR.

The final analyses will be conducted after the final database lock at the end of the study, when all randomized participants have completed the Day 360 visit (or have discontinued from the study). The data snapshot at the time of the final database lock will be used for the final analyses. The analysis cutoff date for the final analyses will be the final database lock date, such that, all collected data will be included in the final analyses. The results from the final analyses will be summarized in the final CSR.

For overall study analyses in core part analyses, available data on or prior to the analysis cutoff date will be used, unless otherwise specified. For by-part analyses, analyses using core part data and extension part data will be performed in core part analyses and final analyses, respectively, unless otherwise specified. If there were any major changes in core part data after the core part DBL, some analyses including only core part data may be repeated in final analyses. This will be recorded in the TFL shell before the final DBL.

In general, continuous data will be summarized using number of non-missing observations (n), mean, standard deviation, median, minimum, the 25th percentile (Q1), the 75th percentile (Q3), and maximum; categorical data will be summarized using frequencies and percentages.

### **2.1.1 General definitions**

#### **Study treatment**

The term “study drug” or “study treatment” refers to the study drug (inclisiran sodium 300 mg s.c. or inclisiran-matching placebo) dispensed during the study.

For each participant and each dosing visit, the participant will be considered to have received the study treatment if the date of dose is non-missing and the answer to ‘was dose administered’ is yes.

For each participant, the first dose date and the last dose date of the study treatment are defined as the earliest date and the latest date on which the participant received the study treatment.

#### **Study day**

Study day will be defined as the number of days since the date of first dose of study treatment. The date of first dose of study treatment will be defined as Day 1 and the day before the first dose of study treatment will be defined as Day -1.

Therefore, for a particular date, study day will be calculated as follows:

For dates on or after the date of first dose of study treatment,

Study day = Assessment date – Date of first dose of study treatment + 1;

For dates prior to the date of first dose of study treatment,

Study day = Assessment date – Date of first dose of study treatment.

In case a participant has been randomized but has not received any study treatment then randomization visit day will be considered as Day 1.

#### **Baseline assessment**

For each variable, the baseline assessment is defined as the last non-missing assessment (scheduled or unscheduled) collected on or prior to the first dose of study treatment, unless otherwise specified. If a participant has never started any study treatment, then the last non-missing assessment (scheduled or unscheduled) collected on or prior to the study Day 1 will be used as baseline assessment.

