6.1.2 Treatment arms/group

At baseline, all participants will be randomized 1:1 to one of the two treatment groups:

- **Inclisiran Group:** 100 participants. Treated with inclisiran sodium 300mg s.c. on Day 1, Day 90 and Day 270, and with matching placebo s.c. on Day 180.
- **Control Group:** 100 participants. Treated with matching placebo s.c. on Day 1 and Day 90, and with inclisiran sodium 300mg on Day 180 and Day 270.

Subcutaneous injections of the Inclisiran/placebo will not be dispensed to the participants but rather administered by qualified personnel at the study site on Day 1, Day 90, Day 180 and Day 270.

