### Switching date

The switching date will be defined using the following algorithm.

- For participants with non-missing Day 180 study treatment dose date, the switching date will be set to the Day 180 study treatment dose date.
- For participants with missing Day 180 study treatment dose date and non-missing Day 180 visit date, the switching date will be set to the Day 180 visit date.
- For participants with missing Day 180 study treatment dose date and missing Day 180 visit date, the switching date will be set to the study day 195 date.

If the resulting switching date locates after the study discontinuation date or the analysis cutoff date (if any), the switching date will be set to missing and the participant will be considered to have not switched until the study discontinuation or the analysis cutoff.

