### 2.7.3 Laboratory data

Laboratory data consists of hematology, biochemistry, and urinalysis measurements. Observed value, absolute change, and percent change from baseline in continuous laboratory parameters will be summarized descriptively by visit and by treatment group. Frequency table of results for categorical laboratory parameters will be presented by visit. For some parameters, only screen tests are planned. Thus, summaries of post-baseline values will not be provided. For core part analyses, the summary tables will include Day 1 visit up to Day 180 visit. For final analyses, the summary table will include Day 1 visit up to Day 360 visit.

Shift tables using the low, normal, or high classification based on the normal range will be used to compare baseline to the worst post-baseline value by treatment group and study part for hematology and biochemistry measurements. All data collected after first dose of study treatment, from scheduled, unscheduled, and premature discontinuation visits will be used. For some parameters, if only screen tests are planned and there are no scheduled post-baseline values, then the shift table will not be provided. In final analyses, OLS will be used for the shift tables of extension part data. Besides, shift tables for overall study will also be provided using SAF.

The following ranges will be used for shift tables of eGFR, fasting glucose and HbA1c

- For eGFR, the categories will be:  
Severe =  $<30 \text{ mL/min}/1.73\text{m}^2$ ;  
Moderate =  $\geq 30 \text{ to } <60 \text{ mL/min}/1.73\text{m}^2$ ;  
Mild =  $\geq 60 \text{ to } <90 \text{ mL/min}/1.73\text{m}^2$ ;  
Normal =  $\geq 90 \text{ mL/min}/1.73\text{m}^2$ .
- For fasting glucose, the categories will be  $< 100 \text{ mg/dL}$ ,  $\geq 100 \text{ mg/dL}$  to  $< 126 \text{ mg/dL}$ , and  $\geq 126 \text{ mg/dL}$ .
- For HbA1c, the categories will be  $<5.7\%$ ,  $\geq 5.7\%$  to  $<6.5\%$ , and  $\geq 6.5\%$ .

For selected laboratory tests, the number and percentage of patients meeting the clinically notable criteria at any time, considering all data collected after first dose of study treatment, from scheduled, unscheduled, and premature discontinuation visits, will be summarized by

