**Table 5-1 Clinically notable laboratory abnormalities for selected tests**

HbA1c criteria is explicitly stated in the table below.

All other criteria are met when both of the following occur:

- Post-baseline values meet the thresholds below
- Baseline values or any previous post-baseline values do not meet the thresholds below

Parameters	Criteria
Hemoglobin	$\leq 10 \text{ g/dL}$
Hematocrit	$\leq 0.8 \times \text{LLN}$
WBC(total)	$\leq 2.8 \times 10^3 / \mu\text{L}$ , $\geq 16 \times 10^3 / \mu\text{L}$

Parameters	Criteria
Platelet count	$\leq 75 \times 10^3 / \mu\text{L}$ , $\geq 700 \times 10^3 / \mu\text{L}$
HbA1c	$\geq 6.5\%$ and $\geq 0.5\%$ increase from baseline
Creatinine	$> 2 \text{ mg/dL}$
CK	$> 1$ and $\leq 3 \times \text{ULN}$
CK	$> 3$ and $\leq 5 \times \text{ULN}$
CK	$> 5$ and $\leq 10 \times \text{ULN}$
CK	$> 10 \times \text{ULN}$

Notable liver function test criteria are defined in [Table 5-2](#).

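### Extension-part laboratory shift tables keep the Control Group's pre-placebo Day 1 baseline, so persisting or recurring placebo-period shifts are counted as shifts on inclisiran

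*SAP*

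**What the plan says.** SAP 2.1.1 defines study treatment as a term that "refers to the study drug (inclisiran sodium 300 mg s.c. or inclisiran-matching placebo) dispensed during the study", so placebo is included. Baseline is the "last non-missing assessment (scheduled or unscheduled) collected on or prior to the first dose of study treatment", unless another rule is given. Protocol 6.1.2 describes the Control Group as "Treated with matching placebo s.c. on Day 1 and Day 90, and with inclisiran sodium 300mg on Day 180 and Day 270".

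SAP 2.7.3 says the shift tables will "compare baseline to the worst post-baseline value by treatment group and study part for hematology and biochemistry measurements", with the Open-label Set (OLS) used for extension-part data. Under the allocation rules in SAP 2.1.1, only values dated after the switching date belong to the extension. A Day 180 pre-dose sample is therefore core-part data and is never the reference value.

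No text in the public SAP sets a second baseline. The one special laboratory baseline, for fasting glucose in SAP 5.3, is a two-value average also anchored at Day 1.

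For clinically notable values, SAP 2.7.3 requires that the baseline *and* any prior post-baseline values did not meet the threshold, with no exception for HbA1c. Table 5-1 uses *or* in the same place and sets HbA1c apart: "HbA1c criteria is explicitly stated in the table below". That criterion is a value of at least 6.5% with a rise of at least 0.5 points from baseline.

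**The concern.** The design is a one-way crossover. The safety of inclisiran monotherapy during the extension is a stated secondary objective. The Control Group is about half of those data and the only group starting inclisiran then. A reader will take its extension shift table as showing what happened on inclisiran, but the reference value predates six months of placebo.

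The error runs both ways. A participant with HbA1c 5.6% on Day 1, 5.8% on Day 180 before any inclisiran and 5.8% on Day 360 appears as an extension worsening. One who is high on Day 1, normal on Day 180 and high again on inclisiran appears as unchanged.

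The SAP handles adverse events differently. Section 2.7.1 counts an extension TEAE only if it starts after the switching date. A persisting adverse event that began on placebo stays in the core part, while a persisting laboratory shift that began on placebo is counted in the extension.

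**Working it through.** The plan gives no figure on this point, so the check is a trace of definitions followed by illustrations.

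**Trace**

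1. Placebo is study treatment (SAP 2.1.1). The Control Group's first dose is placebo on Day 1 (Protocol 6.1.2), so its baseline is a pre-placebo value.
2. Extension values are those after the switching date, normally the Day 180 dose date (SAP 2.1.1).
3. The extension shift table (SAP 2.7.3) therefore compares step 1 with the worst of step 2.
4. Share of the Day 1-to-visit interval spent on placebo = 179/(visit day − 1): Day 210, 179/209 = 85.6%; Day 270, 179/269 = 66.5%; Day 330, 179/329 = 54.4%; Day 360, 179/359 = 49.9%.

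**Which tables depend on it**

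| Table | Affected? |
|---|---|
| Extension shift tables | Yes |
| HbA1c notable criterion | Yes, through the rise from baseline; whether the prior-value condition applies is unclear |
| Combined liver rows (Table 5-2) | Yes: baseline decides which ALT/AST rule applies and enters the ratios for those elevated at baseline |
| Single-parameter liver rows | No: multiples of ULN only |
| Other notable tests | Largely protected by the prior-value condition in SAP 2.7.3 |
| By-visit laboratory and vital-sign tables | Not materially: Day 180 stands beside the later visits |

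**Illustration A: a normal-to-abnormal shift.** Assume 100 Control participants (the planned number), all normal on Day 1. Let *p* be the rate of new abnormality per six months, the same on placebo and inclisiran, and *q* the chance that a placebo-period abnormality is still seen after Day 180. Both are assumptions.

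- Count on the Day 1 baseline = 100pq + 100(1−p)p.
- Count on the Day 180 baseline = 100(1−p)p.

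| p | Day 1 baseline (q = 25% to 100%) | Day 180 baseline |
|---|---|---|
| 2% | 2.5 to 4.0 | 2.0 |
| 5% | 6.0 to 9.8 | 4.8 |
| 10% | 11.5 to 19.0 | 9.0 |
| 20% | 21 to 36 | 16 |

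Carried-over shifts are 20% (0.5/2.5) to 56% (20/36) of those shown. This is the gross error in one direction. It leaves out the opposite error among participants who were abnormal on Day 1.

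**Illustration B: HbA1c categories, both directions.** The SAP cut-points are 5.7% and 6.5%. Assumed: no inclisiran effect, Day 1 mean 5.6% (SD 0.3), assay SD 0.1, between-visit SD 0.1 or 0.2, drift 0 to 0.1 points per six months, one extension value at Day 360.

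| Model | Worse vs Day 1 | Worse vs Day 180 | Excess per 100 |
|---|---|---|---|
| Stationary, SD 0.1, no drift | 10.0% | 9.9% | 0.1 |
| Stationary, SD 0.2, no drift | 14.7% | 14.6% | 0.1 |
| Random walk, SD 0.1, no drift | 10.4% | 8.7% | 1.7 |
| Random walk, SD 0.2, drift 0.1 | 31.1% | 18.8% | 12.3 |

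Across the random-walk settings, 5.1% to 15.7% are worse against Day 1 only and 2.8% to 3.6% against Day 180 only. In the stationary case without drift the two discordant groups are equal, at 4.4% each (SD 0.1) or about 6% each (SD 0.2).

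**The case against.** The strongest reply is that little is hidden. By-visit tables run from Day 1 to Day 360, so placebo-period change in the means is visible. The Control Group's core-part shift table is also reported, and every laboratory value is listed by participant and visit. Only values after the switch count, so a placebo-period change that resolves and stays resolved is not carried over. All this stands and narrows the point. It does not correct the extension shift table, which cross-classifies participants against the wrong reference and has no concurrent inclisiran-naive arm.

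A second reply is that the size is invented: no document gives an HbA1c mean, SD or drift, and the assumed mean sits 0.1 below a cut-point. That also stands. A reader might take the 5% to 16% labelled worse against Day 1 only as bias, but under stationary variation an equal number is missed in the other direction and the net is about zero.

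A reader might also infer that every extension laboratory table mixes placebo and inclisiran time, or that a peak liver signal could be masked. The documents do not support this: single-parameter liver rows use no baseline, and the notable tests other than HbA1c carry the prior-value condition. That condition would not fully settle HbA1c even if it applied. A participant who rose most of the way on placebo and crossed 6.5% by a small step afterwards would still be counted.

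Finally, a Control participant who attends Day 180 but is not dosed is treated as switched at that visit. This is a separate question of period allocation, probably rare, and not part of this point.

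**Conclusion.** The point holds for the Control Group's extension-part shift tables, the HbA1c notable criterion and the combined liver rows. It does not extend to by-visit tables, vital signs, single-parameter liver rows or the guarded notable tests, and it does not touch TEAE allocation or the efficacy analyses.

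The misattribution follows from the definitions and needs no assumption. Its net size does: from about zero to about 12 per 100 Control participants for HbA1c category worsening, according to whether values drift or wander over time or only fluctuate around a stable level. The documents cannot say which. Some SAP text is blacked out, so a baseline rule there cannot be ruled out. This is a cheap and worthwhile improvement to a descriptive analysis of a stated secondary safety objective.

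**What to change.** In SAP 2.1.1, define an extension baseline for the Control Group as the last non-missing value on or before the first inclisiran dose, normally the pre-dose Day 180 sample. Apply it to the extension-part shift tables, the HbA1c criterion and the combined liver rows. Keep Day 1 for all core-part tables and for the Inclisiran Group. The Day 1-referenced Control Group table can be shown alongside.

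- **Fasting glucose:** add a matching rule in SAP 5.3, because the present two-value average is tied to Day 1.
- **Prior-value condition:** reconcile *and* in SAP 2.7.3 with *or* in Table 5-1, and state whether the condition covers HbA1c.
- **Sample availability:** Protocol 1.3 places assessments before dosing, and the schedule shows hematology at Day 180, which includes HbA1c under Table 8-1. The chemistry rows are not in the text available here, so confirm Day 180 chemistry before relying on it for liver, renal and glucose tables.

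The cost is SAP wording and one derived flag. The downside is that the two groups' extension tables will use different reference visits, which needs a footnote. Make the change before the final database lock; if that has passed, add the table and label it as added later.

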#### **Post-baseline assessment**

Post-baseline assessments are defined as those assessments that were collected after the first dose of study treatment.

When change from baseline is of interest the following formula will be used for each scheduled visit and time-point where baseline and post-baseline values are both available:

**Absolute change from baseline** = post-baseline value – baseline value.

**Percentage change from baseline** = (absolute change from baseline / baseline value)\*100.

### Unscheduled assessment

Unscheduled assessments will not be included in by-visit summary but will be included in the derivation of over-period minimum and maximum values.

All scheduled or unscheduled assessments will be included in the listings.

### Early Exist (EE) visit mapping

For participants who discontinued from the study and come to the site for the early exit (EE) visit, the EE visit will be mapped to the next scheduled visit.

**Table 2-1 Early exit (EE) visit mapping**

Study status	Last Attended Scheduled Visit Prior to EE		Mapped Visit for Visit EE	
	Visit Day	Visit Name	Visit Day	Visit Name
Discontinued	1	Visit 1	30	Visit 2
Discontinued	30	Visit 2	90	Visit 3
Discontinued	90	Visit 3	150	Visit 4
Discontinued	150	Visit 4	180	Visit 5/EOC
Discontinued	180	Visit 5/EOC	210	Visit 6
Discontinued	210	Visit 6	270	Visit 7
Discontinued	270	Visit 7	330	Visit 8
Discontinued	330	Visit 8	360	Visit 9/EOS
Completed	---	---	---	---

